### **8.1. Scale and Duration**

The study will be conducted at a maximum of 200 global centers. A maximum of 125 will be located in the US, with the remainder in Canada, Europe, Asia Pacific, Australia and New Zealand. At least 1,780 subjects will be enrolled and successfully implanted with the 4-SITE Lead/Header System. However, any one individual center may not enroll more than twenty percent (20%) of this ceiling without prior approval from Boston Scientific CRM. Investigational centers may continue to enroll patients until the enrollment ceiling is reached or until notified by the Sponsor that study enrollment has been completed.

The entire study will be conducted for approximately eight (8) years; that is, three (3) years for enrollment and five (5) years for follow-up visits. All subjects enrolled in this study must be followed in strict accordance to the investigational plan unless BSC notifies the Investigator to the contrary or BSC has officially terminated/closed the study. Boston Scientific will seek FDA's concurrence to terminate/close the study if both parties determine the circumstances are appropriate for study termination/closure. Study subjects should expect data collection to last five (5) years from implantation. After a subject has completed five (5) years of follow-up, their participation in the study is complete.

Figure 8.1-1: LSS of 4-SITE Study Design

\*NOTE: Not applicable for subjects enrolled post implant.

\*\*NOTE: For subjects enrolled post implant, provide information if available.

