## 10.4. Enrollment Controls

Investigational centers will be notified to cease enrolling patients for this study when the enrollment target is reached, or at the Sponsor's discretion in consultation with the FDA. This notification is expected to happen when at least 1,780 study subjects have been enrolled and successfully implanted with the 4-SITE Lead/Header System. In order to ensure geographical dispersion of investigational sites, individual study sites may not enroll more than twenty percent (20%) of the anticipated enrollment ceiling of 1,780 subjects (*i.e.*, not more than 356 subjects at any single site). For the study overall, no more than 50% of patients will be enrolled post-implant.

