**12.1.3. Hypotheses**

**H0:** The five (5) year chronic lead-related complication-free rate  $\leq 92.5\%$

**HA:** The five (5) year chronic lead-related complication-free rate  $> 92.5\%$

The null hypothesis (H0) will be rejected if the lower one-sided 95% confidence bound for the chronic lead-related complication-free rate is greater than 92.5% (*i.e.*, HA, the alternative hypothesis).

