## **12.3. Data Analyses**

### **12.3.1. Primary Study Endpoint Analysis**

Regarding the 4-SITE Lead and the compatible header in a PG, the primary study endpoint is the evaluation of the proportion of subjects without a chronic 4-SITE Lead/Header-related complication within five (5) years post-implant period. When the final study subject reaches five (5) years of follow-up, the primary analysis will be performed based on the Kaplan-Meier method for the estimation of the five (5) year chronic lead-related complication-free rate, including the lower one-sided 95% confidence interval. The censoring mechanism of the Kaplan-Meier analysis incorporates all available data on study subjects, including those that withdrew or were lost-to-follow-up.

The Kaplan-Meier analysis will begin at the time of implant for each study subject. All subjects who are successfully implanted with the 4-SITE Lead/Header System will be included in the analysis. The endpoint adverse events are defined as complications meeting the criteria described in Sub-section 12.1.2 above. The determination for inclusion of adverse events in the endpoint analysis will be made by an independent Clinical Events Committee (see Sub-section 22.1 hereinafter). Additionally, since this study is focused on chronic 4-SITE Lead/Header System performance, except as noted in Sub-section 12.1.2

above, acute adverse events associated with attempted lead implants will not be included in this analysis. These events fall within the 30 days of an invasive cardiac surgery and do not meet the criteria outlined in Sub-section 12.1.2 above.

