### **12.3.3. Subgroup Analyses**

An analysis will be performed for the primary endpoint to determine whether significant differences exist in endpoint results between subgroups. The list of baseline covariates (with applicable subgroups in parentheses) includes, but is not necessarily limited to, the following:

- Sex (Female vs. Male);
- Geography (International vs. United States);
- Age (< 65 years vs. ≥ 65 years); and
- Enrollment Timing (Pre-Implant versus Post-implant).

The baseline covariate will be added to a univariate logistic regression model and a test for significance at the 5% level will be performed. For each baseline covariate in which a significant difference exists between subgroups, the results for each subgroup will be presented separately.

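### The plan commits to separate subgroup results for the primary endpoint only where a 5% test is significant, so a modest real difference could often go unshown and be overstated when shown

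*Combined protocol and SAP*

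**What the plan says.** Section 12.3.3 (Subgroup Analyses) names four two-level covariates: sex, geography, age and enrollment timing. The list is open; it "includes, but is not necessarily limited to, the following". The test is specified as follows: "The baseline covariate will be added to a univariate logistic regression model and a test for significance at the 5% level will be performed". The display rule comes next: "For each baseline covariate in which a significant difference exists between subgroups, the results for each subgroup will be presented separately".

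No other section commits to subgroup estimates. Section 12.3.2 promises rates and upper bounds for individual adverse events. Section 12.3.6 lists the contents of the progress reports. Neither is broken down by subgroup. No power, expected subgroup difference or multiplicity adjustment is given for these tests.

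Enrollment timing carries particular weight, because Section 10.4 sets the limit that "no more than 50% of patients will be enrolled post-implant". It is the listed covariate that addresses this feature of the design.

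**The concern.** When a result is displayed because it crossed p < 0.05, two things follow if power is low. Real differences of modest size often fail the test, so the plan gives no commitment to show the subgroup rates. Those that pass tend to be the ones that chance has enlarged, so the displayed difference is biased away from zero.

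What is at stake is description, not the main conclusion. The subgroup tables of a post-approval study tell readers whether the complication-free rate is similar in women and men, in older and younger subjects, across regions, and in subjects enrolled before and after implant. A non-significant test alone does not show that two groups are alike. A reader needs both rates and their intervals to judge that.

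**Working it through.** **The plan's own figure.** Section 8.1 gives the sample size: "At least 1,780 subjects will be enrolled and successfully implanted with the 4-SITE Lead/Header System". Its expected rate, power and attrition are redacted in Section 12.1.4, which is not a fault in the plan. The success rule in Section 12.1.3 is that the "lower one-sided 95% confidence bound for the chronic lead-related complication-free rate is greater than 92.5"%. A one-proportion formula with one-sided 5% error is

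n = [(1.645√(p0(1−p0)) + z_power√(p1(1−p1))) / (p1−p0)]².

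With p0 = 0.925, p1 = 0.940 and 80% power, n = [(0.4333 + 0.1999)/0.015]² ≈ 1,782. With p1 = 0.945 it gives 977 (80% power) or 1,316 (90% power) before attrition. Several input sets are therefore compatible with 1,780, and the planned event rate cannot be recovered.

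**Assumptions.** The overall 5-year event rate is 5% (0.05 × 1,780 = 89 events), all 1,780 subjects are evaluable, and the test is two-sided at 5% (the plan does not state sidedness). The higher-risk subgroup has share s = 50%, 30% or 20%, and the true risk ratio is RR = 1.5 or 2. Only the 50% cap on post-implant enrollment comes from the documents.

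**Formulas.** Low-risk rate pL = 0.05/(1 − s + s·RR); high-risk rate pH = RR·pL; d = pH − pL.
- SE1 = √[pH(1−pH)/(1780s) + pL(1−pL)/(1780(1−s))]
- SE0 = √[0.05 × 0.95 × (1/(1780s) + 1/(1780(1−s)))]
- Chance of display = Φ((d − 1.96·SE1)/SE1) with unpooled variance, or Φ((d − 1.96·SE0)/SE1) with pooled variance.

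**Example, RR 1.5, s = 50%.** Rates 4% and 6%, d = 0.0200, SE1 = 0.01032, d/SE1 = 1.938. Chance of display = Φ(1.938 − 1.960) = 49%. The mean z among significant results is about 1.938 + φ(0.022)/0.491 = 2.75, so the overstatement is 2.75/1.938 ≈ 1.42.

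**Example, RR 1.5, s = 20%.** Rates 4.55% and 6.82%, d = 0.02273, SE1 = 0.01446, SE0 = 0.01291. Unpooled: Φ(1.572 − 1.960) = 35%. Pooled: Φ((0.02273 − 0.02531)/0.01446) = 43%.

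The logistic likelihood-ratio test was also simulated (60,000 data sets per setting). The last column is the mean absolute risk difference among significant results divided by the true difference.

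| RR | Share | Rates (low / high) | Unpooled | Pooled | Simulated | Overstatement |
|---|---|---|---|---|---|---|
| 1.5 | 50% | 4.00% / 6.00% | 49% | 49% | 49% | 1.41 |
| 1.5 | 30% | 4.35% / 6.52% | 43% | 49% | 46% | 1.48 |
| 1.5 | 20% | 4.55% / 6.82% | 35% | 43% | 39% | 1.62 |
| 2 | 50% | 3.33% / 6.67% | 90% | 90% | 91% | 1.06 |
| 2 | 30% | 3.85% / 7.69% | 85% | 90% | 90% | 1.06 |
| 2 | 20% | 4.17% / 8.33% | 76% | 85% | 84% | 1.10 |

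The quoted ranges, 35–49% and 76–90%, span the two formulas. The simulated values lie within them to about one percentage point.

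**Sensitivity.** Take event rates of 2.5%, 5% and 7.5%, with 1,780 or 1,100 evaluable subjects and the same three shares. The pooled formula then gives 19–67% for RR 1.5 (overstatement 1.2–2.9 times) and 43–98% for RR 2 (1.0–1.7 times). RR 1.5 exceeds 50% only at a 7.5% event rate with 1,780 subjects. RR 2 falls below 50% only at a 2.5% rate with 1,100.

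**No true differences.** Four independent 5% tests give 1 − 0.95⁴ = 18.5% as the chance that at least one covariate is displayed.

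**The case against.** The strongest reply is that the section does not contain the word 'only' and prohibits nothing. It commits to an analysis and a test for every listed covariate, so the odds ratio and p-value will exist for all of them and may well be reported. Section 12.3.2 refers to a Statistical Analysis Plan that can be amended before analysis, and table layouts may be settled there. This stands: the point concerns what the plan commits to, and the restriction is read from its silence elsewhere. That silence is still worth closing, because the one written trigger for showing subgroup results is significance.

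A reader might go further and infer that real subgroup differences will usually be hidden and that any shown will be exaggerated. The documents do not support that. Under the assumptions above a doubling of risk would usually be displayed, with an overstatement of only 1.06–1.10 times, and for RR 1.5 some plausible inputs give better than even odds. A reader might also infer that the plan treats a non-significant test as proof of consistency. Section 12.3.3 draws no such conclusion.

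It can also be said that this is secondary reporting in a single-arm study. That is correct and limits the severity. Neither the Kaplan-Meier estimate in Section 12.3.1 nor the success rule in Section 12.1.3 depends on the subgroup display.

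**Conclusion.** The point holds for modest differences. Section 12.3.3 ties separate subgroup results to p < 0.05, and the plan commits to them nowhere else. At a 5% event rate with 1,780 evaluable subjects, a true risk ratio of 1.5 would be displayed somewhat less than half the time (about 35–49%) and overstated by about 40% to 60% when it is. For a doubling of risk the problem is small.

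These sizes depend on event rates, evaluable numbers, subgroup shares and risk ratios that the public documents do not give; fewer events would make the selection stronger and more would make it weaker. The primary test is unaffected. This is a cheap improvement of low severity.

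**What to change.** Replace the last sentence of Section 12.3.3 with:

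> For every listed covariate, the 5-year Kaplan-Meier complication-free rate with its confidence interval will be presented for each subgroup, with the estimated between-subgroup effect and its confidence interval from the planned model, regardless of significance; these estimates are descriptive and not adjusted for multiplicity.

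Taking the effect from the planned logistic model avoids adding a hazard ratio as a second effect measure for the same comparison. The 5% test can stay, but it no longer decides what is shown, so selection on significance disappears for these covariates.

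The cost is eight subgroup estimates (four covariates with two levels each) and four effect estimates, plus the note on multiplicity. No new data or subjects are needed. Section 12.3.2 already provides the route: an amended Statistical Analysis Plan approved before the analyses are run.

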### **12.3.4. Center Pooling Analysis**

Center-to-center heterogeneity will be assessed for the primary endpoint by performing a random effects logistic regression analysis. Centers will be deemed to be heterogeneous if the variance of the random center effect is found to significantly differ from zero. A significance level of 10% will be used for this test.

### **12.3.5. Trend Analysis**

BSC trend management procedures provide criteria for initiating trend analysis and will be utilized in conjunction with data collected in this study. Device performance information is received from many sources through various channels including clinical studies and device registries. BSC also monitors product performance information from many sources including suppliers, testing, manufacturing, clinicians, physicians, patients and field-based personnel to identify opportunities for product improvement. When a device is returned to BSC,

laboratory technicians and engineers assess overall device function and perform analyses using specific tests related to the clinical observation(s). Test results are compared to the original manufacturing records and design intent. Clinical observations are added to laboratory findings to help determine the root cause of the clinical observation(s). Each discrete event is then compared to other similar-appearing events. If a pattern is detected, actions are taken to identify a common root cause, and device enhancements that are focused on improving product reliability may be implemented. Improvements, when implemented, may include design changes to the existing products or to subsequent generations, manufacturing and supplier process modifications, software updates, educational communications and/or labeling changes, for example.

### **12.3.6. Progress Reporting Analysis**

Progress reports to the FDA will be provided by the Sponsor every six (6) months. These reports will generally include:

- A summary of enrollment and lead status;
- A Kaplan-Meier plot of time to first endpoint-defined chronic 4-SITE Lead/Header System-related complication;
- A summary of trend analysis; and
- A summary of RV lead and header-related adverse events.

### **12.3.7. Product Performance Reporting**

In order to share information learned from this study with practitioners on an on-going basis, data will be published in a BSC Product Performance Report. However, this will occur no sooner than one (1) year post study initiation when at least 200 subjects are participating in the study and who have implanted with the 4-SITE Lead/Header System and when at least 50 subjects having reached a reporting interval in the United States.

## **13. Data Management**

### **13.1. Data Collection, Processing and Review**

Study subject data will be recorded in a limited access secure electronic data capture (EDC) system provided by the Sponsor.

The clinical database will reside on a production server hosted by Medidata Solutions (New York, NY). All changes made to the clinical data will be captured in an electronic audit trail and available for review by Boston Scientific Corporation (BSC) or its representative. The associated RAVE software application and database have been designed to meet regulatory compliance for deployment as part of a validated system compliant with laws and regulations applicable to the conduct of clinical studies pertaining to the use of electronic records and signatures. Database backups are performed on a regular basis.

For the LSS of 4-SITE Study, all data will be entered into electronic case report forms (eCRFs) that are located on BSC's study electronic data capture system (EDC). Study subjects' medical records/charts serve as source documentation for electronically entered data.

Center personnel are required to conduct an active study subject review of medical records/charts (*e.g.*, involving implantation, subject discharge and any subsequent in office follow-up visits) to ensure the capture of all possible adverse events during and between study subject follow-up visits. Following thorough review of each study subject's medical records/charts, site/center research personnel are asked whether adverse events were identified by answering a designated questionnaire on the corresponding case report form. Site/center research personnel verify whether any of the reportable adverse events as described in Sub-section 12.1.2 and Section 18 have occurred.

The Investigator provides his/her electronic signature on the appropriate electronic case report forms (eCRFs) in compliance with local regulations. A written signature on printouts of the eCRFs must also be provided if required by local regulation. Changes to data previously submitted to the Sponsor require a new electronic signature by the Investigator acknowledging and approving the changes.

Visual and/or electronic data review will be performed to identify possible data discrepancies. Manual and/or automatic queries will be created in the EDC system and will be issued to the site for appropriate response. Investigational site staff will be responsible for resolving all queries in the database.

### **13.2. Data Retention**

The Investigator will maintain, at the investigative site, in original format all essential study documents and source documentation that support the data collected on the study subjects in compliance with ICH/GCP guidelines. Documents must be retained for at least two (2) years after the last approval of a marketing application or until at least two (2) years have elapsed since the formal discontinuation of the clinical investigation of the product. These documents will be retained for a longer period of time by agreement with BSC or in compliance with other local regulations. It is BSC's responsibility to inform the Investigator when these documents no longer need to be maintained. The Investigator will take measures to ensure that these essential documents are not accidentally damaged or destroyed. If for any reason the Investigator withdraws responsibility for maintaining these essential documents, custody must be transferred to an individual who will assume responsibility and BSC must receive written notification of this custodial change.

### **13.3. Case Report Forms**

#### **13.3.1. Enrollment Case Report Form**

An Enrollment Case Report Form is completed when a study subject has completed their enrollment visit and all required data collection is complete.

**13.3.2. Implant Case Report Form**

An Implant Case Report Form is completed at the device system implant of a study subject or at post-implant enrollment, as applicable. All required data collection must be completed.

**13.3.3. Pre-Discharge Case Report Form**

A Pre-Discharge Case Report Form will be completed to record all lead measurements collected at the time of hospital/center discharge. For study subjects enrolled post-implant, this data is requested, but not required. An active medical records/charts review will be conducted to identify all adverse events, as defined in Sub-section 12.1.2 and Section 18.

**13.3.4. One-Month Follow-up Case Report Form**

A One-Month Follow-up Case Report Form will be completed to record all lead measurements collected during this study subject follow-up visit. An active medical records/charts review will be conducted to identify all adverse events, as defined in Sub-section 12.1.2 and Section 18.

**13.3.5. Bi-Annual Follow-up Case Report Form**

The Bi-Annual Follow-up Case Report Form will be completed every six (6) months (+/- 30 days) to record all lead measurements collected during this study subject follow-up visit. These forms are labeled by visit within the EDC system (*e.g.*, 6-Month Follow-up, 12-Month Follow-up, etc.). An active medical records/charts review will be conducted to identify all adverse events, as defined in Sub-section 12.1.2 and Section 18.

**13.3.6. Unscheduled Visit Case Report Form**

In the event of an unscheduled study subject visit, an Unscheduled Visit Case Report Form will be completed to provide the reason for the visit and record any adverse events, as defined in Sub-section 12.1.2 and Section 18.

**13.3.7. Adverse Event Case Report Form**

Upon discovery of an adverse event with a study subject, an Adverse Event Case Report Form must be completed to record any adverse events, as defined in Sub-section 12.1.2 and Section 18.

**13.3.7.1. Additional Information Collected at Device System Revision/Replacement or Upgrade**

Should study subjects undergo surgical intervention for lead or pocket revision/reposition, this information is captured on the Adverse Event Case Report form. In the event of a 4-SITE RV lead revision, a detailed assessment of the proximal end of the lead and the header at lead revision/reposition should be completed. The investigator should also document any lead damage.

**13.3.8. Device Deficiency Case Report Form**

In the event a device deficiency (as defined in the protocol (Table 20.1-1)) is identified, a Device Deficiency Case Report Form will be completed.

**13.3.9. End of Study Case Report Form**

An End of Study Case Report Form will be completed when a study subject is no longer active in the LSS of 4-SITE Study. Reasons for a change in study subject status include study completion, death and withdrawal.

The status of the 4-SITE lead must be reported at the time of subject withdrawal from the study.

**13.3.10. Explanted and Out-of-Service Device Case Report Form**

For any implanted devices which are explanted and/or taken out of service (whether capped or removed), the Explanted and Out-of-Service Case Report Form must be completed.

**NOTE :** If the 4-SITE RV lead is explanted and/or taken out of service, the study subject must be withdrawn from the study.

**13.3.11. Deviations Case Report Form – Definition & Major Reasons**

Protocol deviations are defined as any divergence from the study protocol. Reasons for a deviation include, but are not limited to, the following: study subject consent not obtained, testing incomplete/not performed, and/or follow-up outside the scheduled protocol required follow-up visit window. Study protocol deviations are further clarified in Section 15

**13.4. Additional Information Collected at Suspected Lead Failure**

If the reason for study subject withdrawal is lead failure, supporting objective evidence is required. Objective evidence includes, but is not necessarily limited to, the following: Pacing System Analyzer (PSA) measurements demonstrating lead performance (thresholds, impedance, and/or sensing), stored EGMs, cine recordings and/or radiographic evidence. Techniques such as pocket manipulation, arm maneuvers, valsalva maneuver, coughing and/or exploration of potential sources of external magnetic interference (EMI) may be used to detect system abnormalities, at the discretion of the Investigator. Please refer to Sub-section 26.2 hereinafter for suggested suitable confirmation information depending on the lead failure mode.

A detailed assessment and report by the explanting Investigator/ Physician of the proximal end of the lead and the header at device change-outs is required. Data collected during explant of a lead will also be required, including extraction method and tools/instruments

used.

**NOTE:** For US and Canadian site personnel, please make every attempt to return explanted product to the manufacturer. Boston Scientific provides a *Returned Products Kit* (Model #6499) that can be requested through BSC's Customer Service Department at [name], by phoning [name] or by submitting an online request at: [www.bostonscientific.com/ppr](http://www.bostonscientific.com/ppr). Site representatives from Other Countries should please contact the local Boston Scientific office and/or affiliate for assistance (contact information may be found at the BSC website: [www.bostonscientific.com/home.bsci](http://www.bostonscientific.com/home.bsci)).

